4.1. PLGS Pilot Period Overview

522
523
524
525
526

Prior to the initiation of the crossover trial, 10 adult participants will use the study CGM and Tandem's t:slim X2 with Basal-IQ Technology system that includes the predictive low glucose suspend function (referred to subsequently as "Tandem PLGS pump") in a 10-day Pilot Period. Data will be evaluated for system usability and predetermined safety metrics before participants ≥ 12 years old may be randomized into the crossover trial.

527

528

4.2. Initiation of PLGS

529
530
531

Participants will be trained on the use of the PLGS feature of the pump and instructed to use the Tandem PLGS pump and study CGM daily until returning to the clinic. Participants will be provided with all CGM and pump supplies, including insulin if needed.

532

533

4.3. Visit and Contact Schedule

534
535

Contact via phone, email, or text will occur on days 1, 2, and 5 (± 1 day) to assess for adverse events and system issues.

536

537
538
539
540

Participants will use the PLGS system for at least 10 days and then return to the clinic after 10+4 days. Participants may use commercially available features of the study CGM system related to mobile data access or remote monitoring, but will be instructed not to use any third-party components for this purpose.

541

542
543
544
545

Device data will be downloaded at the day 10 clinic visit. Participants will be transitioned to a study Tandem SAP pump (no PLGS feature) and may continue study CGM use until data review from all Pilot Period participants has been completed. Participants will then return to the clinic to participate in the crossover trial as described below when that part of the study begins.

546

547

4.4. PLGS Pilot Period Data Review

548
549

After the 10th participant completes the Pilot Period, data from approximately 100 participant-days will be evaluated for system usability and predetermined safety metrics.

550

551

Predetermined safety metrics are the following:

552

553

- No PLGS-related DKA
- No severe hypoglycemia related to system malfunction

554

555
556
557
558

All instances of DKA or severe hypoglycemia will be adjudicated by the Medical Monitor to determine whether the events were related to system performance. If the predetermined safety metrics are not satisfied, the study will be stopped for system evaluation as described in Section 8.6.

559

560
561
562
563

Usability will be assessed on participant and investigator feedback. If system changes are required due to safety or usability issues, any necessary regulatory or IRB reviews will be performed. Then the Pilot Period will be repeated, and the results will again be evaluated for safety and usability prior to the crossover trial.

CHAPTER 5: CROSSOVER TRIAL

5.1. Crossover Trial Overview

The main part of the study, a six-week crossover trial, consists of two arms which will receive different treatments. Participants will be randomly assigned to one treatment option, then cross over to the other treatment option after three weeks. The two treatment options are:

- Intervention (PLGS Group): Use of the Dexcom G5 CGM with an insulin pump that has a PLGS feature (t:slim X2 with Basal-IQ Technology)
- Control (SAP Group): Use of the Dexcom G5 CGM with an insulin pump that does not have a PLGS feature (t:slim X2 Dexcom G5 Mobile CGM Enabled)

The two Tandem pumps, referred to as the Tandem PLGS and the Tandem SAP pumps, respectively, are identical in functionality and user interface (UI) with the exception of the PLGS feature and associated UI component.

5.2. Crossover Trial Initiation

The crossover trial will begin after successful completion of the Pilot Period (see Chapter 4).

Initially, participants ≥ 12 years old can be entered into the crossover trial. Initiation of the crossover trial by participants 6 to 11 years old will be deferred until data from 100 post-randomization PLGS participant-days have been evaluated from participants 12 to 17 years old (of which at least 50 participant-days will come from participants 12 to <15 years old) and the same predetermined safety metrics used to evaluate the Pilot Period have been satisfied.

- If the safety criteria to proceed to the younger age group are not met, then there will be a hold on initiating the crossover trial in this age group until either additional data are collected from the active participants or a revision is made to the risk mitigation plan and approved by FDA before proceeding

Randomization into the crossover trial may be restricted to participants with at least 3% of sensor glucose values <70 mg/dL during an approximately two-week period prior to randomization if the crossover trial is projected to include fewer than 75% of such participants.

5.2.1. Crossover Study Periods

- Study Period 1: 3-week period of PLGS (Group A) or SAP (Group B)
- Study Period 2: 3-week period of PLGS (Group B) or SAP (Group A)

5.3. Home Procedures during the Study Periods

During the two study periods, participants will be asked to:

- Use the study pump and study CGM every day
- Keep the PLGS feature activated if using the Tandem PLGS pump
- Not change pump settings related to insulin delivery (such as basal rate, correction factor, and carb ratio) without first discussing with study staff
- Ensure proper calibration of the CGM at all times, using the study-provided glucose meter
- Measure blood ketones with the study-provided ketone meter when CGM glucose is >300 mg/dL on awakening or for at least one hour at other times, or >400 mg/dL at any time. CGM glucose >300 mg/dL should be confirmed by self-monitoring of blood glucose (SMBG) readings
- Participants may use commercially available features of the study CGM system related to

611 mobile data access or remote monitoring, but will be instructed not to use any third-party
612 components for this purpose. Participants will be encouraged to be consistent with their use of
613 any such features between the two periods of the crossover study.

614 • Contact the study staff if:

615 ○ Blood ketone readings are ≥ 1.5 mmol/L
616 ○ There are any technical issues with the system
617 ○ There are any symptoms or occurrences of DKA, severe hypoglycemia, or development
618 of other medical problems
619 ○ Pregnancy is possible
620 ○ Discontinuation of study participation is desired

621 Participants will also receive study staff contact information to ask any questions they may have during
622 the study.

623 **5.4. Prohibited Medications, Treatments, and Procedures**

624 Participants will be instructed that acetaminophen must be avoided during the study. If acetaminophen
625 is inadvertently taken, the participant will be instructed to disable the PLGS feature for 4 hours and to
626 not use the CGM measurements for diabetes management during this time.

627 Participants will be instructed not to add any new glucose-lowering agents during the study.

628 **5.5. Study Visits and Contacts**

629 The schedule for follow-up visits and contacts is the same during both periods of the crossover trial.

630 • 2 ± 1 day: Contact via phone, email, or text
631 • 7 ± 2 days: Visit
632 • 14 ± 3 days: Contact via phone, email, or text
633 • 21 ± 7 days: Visit

634 At each contact and visit, the occurrence of device issues and adverse events will be solicited. Device
635 data will be uploaded at the day 7 visit (and from home if possible) and are needed to assess issues that
636 may arise.

637 Additional visits and contacts may occur at investigator discretion.

638 **5.6. Crossover Trial Randomization Visit (Beginning of Study Period 1)**

639 The following procedures will be completed at the crossover trial randomization visit:

640 • Eligibility criteria will be reviewed to verify that there have been no changes that could affect
641 eligibility since enrollment
642 • The individual's understanding of the protocol and willingness to participate in the crossover
643 trial will be reviewed
644 • HbA1c will be measured using the DCA Vantage or similar point-of-care (POC) device or local
645 lab if not already measured on the same day during the screening visit
646 • A pregnancy test will be performed if not already performed on the same day during the
647 screening visit
648 • All needed study supplies will be given to the participant

649 Study personnel will enter data on the study website to verify eligibility and obtain random assignment

658 to Group A or Group B
659 • Group A: intervention period first (PLGS), control period second (SAP)
660 • Group B: control period first (SAP), intervention period second (PLGS)

661
662 Group A participants will receive PLGS training (if not previously received through participation in
663 the Pilot Period).

664

665 **5.6.1. End of Study Period 1 Follow-up Clinic Visit and Beginning of Study Period 2**

666 The following procedures will occur during this visit:

- 667 • Data will be reviewed for potential safety issues, and if none pump settings will not be adjusted
668 prior to initiation of Study Period 2
- 669 • HbA1c level will be measured using the DCA Vantage or similar point-of-care device or local
670 lab
- 671 • Group A participants will complete the PLGS usability survey (see Chapter 7)
- 672 • Initiation of Study Period 2
 - 673 ○ Group A participants will return the Tandem PLGS pump and receive the Tandem SAP
674 pump with all needed supplies.
 - 675 ○ Group B participants will return the Tandem SAP pump and receive the Tandem PLGS
676 pump with all needed supplies, and will receive training (or refresher training if applicable)
677 on the PLGS feature of the pump.

678

679 **5.6.2. End of Study Period 2 and Final Visit**

680 The following procedures will occur at the end of Study Period 2:

- 681 • Data will be reviewed for potential safety issues
- 682 • HbA1c level will be measured using the DCA Vantage or similar point-of-care device or local
683 lab
- 684 • Group B participants will complete the PLGS usability survey (see Chapter 7)
- 685 • All applicable study supplies will be returned to the clinic

688 CHAPTER 6: STUDY DEVICES

689

690 6.1. Description of the Investigational Device

[figure not shown]
691 6.1.1. Insulin Pump

692 The Tandem Diabetes ambulatory infusion pump with PLGS (t:slim X2 with Basal-IQ Technology) is
693 intended for the subcutaneous delivery of insulin for the management of diabetes mellitus in persons
694 requiring insulin. A touch sensitive Liquid Crystal Display (LCD) provides both the pump information
695 to the user as well as the interface for the user to program insulin delivery timing and quantity, both
696 basal and bolus delivery of insulin at set and variable rates.

697 Additionally these pumps are integrated with and display continuous glucose data (CGM) and contain
698 a Predictive Low Glucose Suspend (PLGS) algorithm which allows the user to set the system to
699 automatically suspend delivery of insulin when the predicted glucose value falls below a predefined
700 threshold.

702 The device system components include an insulin pump and cartridge, infusion catheter, CGM sensor
703 and transmitter, and a blood glucose meter for CGM calibrations.

705 706 Figure 3 - Tandem Pump Showing Labeled Components

707 708 709 6.1.2. Continuous Glucose Monitoring

710 The study CGM will include an unmodified Dexcom G5 Mobile transmitter and sensors. This is an
711 FDA-approved device system with no changes to its hardware or firmware components. The CGM
712 sensor will be replaced at least once every seven days.

713 714 6.1.3. Blood Glucose Meter and Strips

715 Blood glucose levels will be measured and the CGM device will be calibrated using the Accu-Chek
716 Guide Blood Glucose Monitoring System in accordance with the manufacturer labeling.

717 718 6.1.4. Ketone Meter and Strips

719 Blood ketone levels will be measured using the Abbott Precision Xtra meter and strips in accordance
720 with the manufacturer's labeling. The blood glucose meter component of the Precision Xtra device will
721 not be used.

722

723 **6.2. Study Device Accountability Procedures**

724 Device accountability procedures will be detailed in the study procedures manual.

725

726 **6.2.1. Blood Glucose Meter Testing**

- 727 • Participants will be provided with instructions to perform QC testing per manufacturer
728 guidelines.
- 729 • All study blood glucose meters will be QC tested with at least two different concentrations of
730 control solution if available during all office visits. A tested meter will not be used in a study if
731 it does not read within the target range at each concentration per manufacturer labeling. The
732 Participant will be instructed to contact study staff for a replacement of the meter, test strips,
733 and control solution if a meter fails QC testing at home.
- 734 • Participants will be reminded to use the study blood glucose meter for all fingerstick blood
735 glucose measurements
- 736 • Participants will be asked to perform fingerstick blood glucose measurements in accordance
737 with the labelling of the study CGM device.

738

739 **6.2.2. Blood Ketone Testing**

- 740 • Participants to perform QC testing at home per manufacturer guidelines.
- 741 • All study blood ketone meters will be QC tested with at least two different concentrations of
742 control solution if available during all office visits. A tested meter will not be used in a study if
743 it does not read within the target range at each concentration per manufacturer labeling. The
744 Participant will be instructed to contact study staff for a replacement of the meter, test strips,
745 and control solution if a meter fails QC testing at home.
- 746 • Participants will be instructed on how to perform blood ketone testing
- 747 • Participants will be given guidelines for treatment of elevated blood ketones

748

749 **6.3. Safety Measures**

750 **6.3.1. CGM Calibration**

751 Throughout the study, participants will be instructed to calibrate the study CGM in accordance with
752 manufacturer labelling.

753 **6.3.2. PLGS Suspend and Resume Alerts**

754 By default, the Tandem PLGS pump's audible PLGS suspend and resume alerts will be disabled when
755 the participant receives the pump. The participant will be permitted to enable these audible alerts if
756 desired during system use.

757 **6.3.3. Low Glucose Alert and Safety Protocol**

758 Participants will be required to set the CGM low glucose alert level between 60 mg/dL and 70 mg/dL
759 during the course of the study, and not to change this setting during the crossover trial.

760 If a participant receives a CGM low glucose alert or notes that the CGM glucose is below the low
761 glucose threshold alert value, confirmatory fingerstick testing will be performed if required by CGM

765 labelling and the participant will be instructed to treat hypoglycemia with ~16 grams of fast-acting oral
766 glucose.

767

768 **6.3.4. High Glucose Alert and Safety Protocol**

769 Participants will be required to set the CGM high glucose alert level between 200 mg/dL and 300
770 mg/dL during the course of the study, and not to change this setting during the crossover trial.

771

772 If a participant receives a CGM hyperglycemia threshold alert or notes that the CGM glucose is above
773 the hyperglycemia threshold alert value, confirmatory fingerstick testing will be performed if required
774 by CGM labelling.

775

776 If a participant's CGM reading is ≥ 300 mg/dL when fasting in the morning upon awakening, ≥ 300
777 mg/dL for over 1 hour during the day, or ≥ 400 mg/dL at any point, the participant will be instructed to
778 take the following steps:

779

- 780 • Perform a blood glucose meter check.
- 781 • If the blood glucose is ≥ 300 mg/dL, then blood ketones should be measured with the study
ketone meter.
- 782 • Correction insulin may be taken per the participant's usual routine.
- 783 • Participants will be instructed to change their pump site and administer correction insulin via
784 insulin syringe or pen for ketones ≥ 0.6 mmol/L and to additionally notify study staff for
785 ketones ≥ 1.5 mmol/L.

CHAPTER 7: TESTING PROCEDURES AND QUESTIONNAIRES

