58 may be randomized into the crossover trial. Immediately after randomization, subjects will enter the two
59 3-week study periods (21 days each) and will test one intervention per study period, using either the
60 PLGS or SAP system first. The interventions will not be separated by a washout period.
61

62 **2. Statistical Hypotheses**

- 63 • *Null Hypothesis*: There is no difference in the mean time spent below 70 mg/dL over the 21-day
64 period between the two treatment groups.
- 65 • *Alternative Hypothesis*: There is a nonzero difference in the mean time spent below 70 mg/dL
66 over the 21-day period between the two treatment groups.
67

68 **3. Sample Size**

69 The study is projected to include at least 90 subjects. Of these study participants, at least 45 will be $<$ 18
70 years old, and at least 45 will be \geq 18 years old. Of the 45 participants that are $<$ 18 years old, at least 15
71 participants will be 12 to 17 years old, and at least 15 will be 6 to 11 years old. The 90 study participants
72 will also include a minimum of 15 pump users, 15 multiple daily injection of insulin (MDI) users, 15
73 CGM naïve users (may be pump or MDI users), and 15 experienced CGM users (may also be pump or
74 MDI users).
75

76 The subjects will be randomized to the order of the interventions based on a 1:1 ratio. Randomization
77 will not be stratified.
78

79 **4. Outcome Measures**

80 **4.1 Primary Efficacy Endpoint:**

81 Percent of CGM glucose sensor values < 70 mg/dL

83 **4.2 Secondary Efficacy Endpoints:**

84 *CGM Metrics*

85 Overall Glucose Control

86 1) Mean of CGM glucose sensor values

87 2) Percent of CGM glucose sensor values between 70 and 180 mg/dL (not inclusive of the
88 limits)

89 Hypoglycemia

90 3) Percent of CGM glucose sensor values < 60 mg/dL

91 4) Percent of CGM glucose sensor values < 50 mg/dL

92 5) Area over curve for CGM glucose sensor values < 70 mg/dL.

93 6) Low blood glucose index (LBGI).

94 7) Frequency of CGM-measured hypoglycemic events per week (see below)

95 Hyperglycemia

96 8) Percent of CGM glucose sensor values > 250 mg/dL

97 9) Percent of CGM glucose sensor values > 180 mg/dL

98 10) Area under curve for CGM glucose sensor values > 180 mg/dL.

99 11) High blood glucose index (HBGI)

101 **4.3 Calculation of CGM Metrics**

102 Each metric will be calculated for CGM sensor values over the entire 24-hour period.

103

104 Primary Outcome - % Time Below 70 mg/dL

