105 The percentage of glucose sensor values <70 mg/dL will be calculated for each participant in each 3-
106 week treatment period by pooling all glucose sensor readings that occur within each 3-week period.

107 Available CGM data will be included in the calculation based on when the subject completes the study
108 visits. If exact date-times of when patient left the clinic on study period initiation visits are available,
109 then the study windows for CGM data inclusion are defined as:

111

	Includes All Available CGM data from:	
	Start Date	Last Date
Period 1	Date-time in which patient left clinic on Period 1 Initiation Visit	Earlier of: a) Date-time in which patient left clinic on Period 1 Initiation Visit + 21 full days, or b) Date-time in which patient left clinic on Period 2 Initiation Visit
Period 2	Date-time in which patient left clinic on Period 2 Initiation Visit	Earlier of: a) Date-time in which patient left clinic on Period 1 Initiation Visit + 21 full days, or b) Final Visit

112

113 Otherwise, in the case of a protocol deviation and the above information is not available, the study windows are defined as:

115

	Includes All Available CGM data from:	
	Start Date	Last Date
Period 1	Randomization Visit +1	Earlier of: a) Randomization Visit + 22 Days, or b) Period 2 Initiation Visit
Period 2	Period 2 Initiation Visit +1	Earlier of: a) Period 2 Initiation Visit + 22 Days, or b) Final Visit

116

117 All glucose sensor readings will be weighted equally in the pooled percentages regardless of how they distribute across weeks. Data will not be truncated due to protocol deviations.

119

120 **Secondary CGM Metric Outcomes**

121 All secondary CGM metrics will be calculated analogously as described above for the primary outcome.

122

123 **PLGS and CGM Use**

124 Number of hours of CGM/PLGS use per week will be calculated as the sum of the time intervals between readings, excluding calibration readings. If an actual time interval is greater than the device's default time interval, then that time interval will be set to the device's default time interval. Number of hours of CGM and PLGS use will be expressed as a percentage of the total number of hours in a week.

128

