129 Total percentage of time PLGS and CGM is used per week will be calculated by dividing the total number of hours of PLGS readings by the maximum possible number of hours within the study period visit dates described above. Number of days of PLGS and CGM use per week is calculated as the count

132 of days during the week where there was at least one PLGS/CGM reading. Data from both study periods
133 will be included in this analysis. No missing data will be imputed.

134

135 **Hypoglycemic Events**

136 A CGM-measured hypoglycemic event will be defined as:

- 137 • at least 2 sensor values < 54 mg/dl
- 138 • that are 15 or more minutes apart
- 139 • no intervening values > 54 mg/dl
- 140 • Event ends when:
 - 141 ➤ at least 2 sensor values > 70 mg/dl
 - 142 ➤ that are 30 or more minutes apart
 - 143 ➤ no intervening values < 70 mg/dl
- 144 • Participant becomes eligible for a new event as soon as the above criteria for ending the previous
145 event have been met.

146

147 **5. Description of Statistical Methods**

148

149 **5.1 General Approach**

150 All analyses will compare the 3-week period of PLGS to the 3-week period of SAP and will follow the
151 intention-to-treat principle with each period analyzed according to the treatment assigned by
152 randomization regardless of actual PLGS or SAP utilization. All participants who have at least one
153 CGM reading in each 3-week period will be analyzed for the primary and secondary outcomes. All p-
154 values will be two-sided.

155

156 Standard residual diagnostics will be performed for all analyses. If values are highly skewed, then a
157 transformation or nonparametric methods will be used instead. Previous experience suggests that a
158 transformation may be necessary for the hypoglycemic and hyperglycemic outcomes. We do not expect
159 that a transformation will be necessary for some overall glucose control metrics (such as mean glucose).

160

161 **5.2 Analysis Cohorts**

- 162 • All randomized participants who have at least one CGM reading in both 3-week periods will be
163 analyzed for the Intention-to-Treat (ITT) Analysis with each day included in the treatment group
164 assigned by randomization.
- 165 • Safety outcomes will be reported for all enrolled participants, irrespective of whether the study was
166 completed.
- 167 • A per-protocol analysis will be restricted to participants with ≥ 200 hours of CGM data in each 3-

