168 week period. This analysis will only involve the primary outcome, and will only be done if at least
169 10% of subjects are excluded based on this criterion.

170

171 **6. Analysis of the Primary Efficacy Endpoint**

172

173 **6.1 Included Subjects**

174 As noted in section 5.2, the primary analysis for this study will include all randomized subjects with at
175 least one CGM sensor reading in each of the two treatment periods. No additional minimum amount of
176 CGM use is required otherwise.

177

178 **6.2 Missing Data**

179 There will be no imputation of missing CGM data for the primary analysis in this study.

180

181 **6.3 Statistical Methods**

182 Mean \pm SD (standard deviation) or summary statistics appropriate to the distribution will be reported for
183 % time below 70 mg/dL for each treatment arm. A repeated measures regression model with an
184 unstructured covariance structure will be fit for percent time below 70 mg/dL to compare the two
185 treatments. The model will adjust for period as a covariate.

186

187 Residual values from the above model will be examined for an approximately normal distribution. It is
188 likely that the residuals themselves will have a skewed distribution, but that the paired differences from
189 the same subject may follow an approximate bell-shaped curve. However, if the paired differences have
190 a skewed distribution, then an appropriate transformation or a nonparametric analysis based on ranks
191 will be performed. Significance will be assessed at the 5% level.

192

193 A carryover effect is not expected, but it will be assessed with a separate model built with the inclusion
194 of a period by treatment interaction. However, the study is not expected to have sufficient power in
195 making definitive conclusions about the period by treatment interaction.

196

197 **7. Analysis of the Secondary Endpoints**

198 The same subjects will be included as in the primary analysis. Missing data will not be imputed for any
199 of the secondary analyses in this study.

200

201 **7.1 Statistical Methods**

202 For all secondary outcomes, summary statistics appropriate to the distribution will be tabulated by
203 treatment group. Analysis of all secondary endpoints will parallel the primary analysis. A ranked normal
204 score transformation will be applied to all highly skewed secondary outcomes.

205

206 **7.2 Secondary Analyses by Time of Day**

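### The visit that ends each treatment period has two incompatible windows: day 21 to 28 in Protocol Table 1, day 14 to 28 in Protocol Section 5.5

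*Protocol*

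**What the plan says.** **Visit window.** In Protocol Table 1 the end-of-period visit is timed at 21+7d. The other three follow-up cells in that row use ±. Protocol Section 5.5 lists the same visit as "21 ± 7 days: Visit". Its other three entries, for example "14 ± 3 days: Contact via phone, email, or text", agree with Table 1. Only the visit that closes a period differs.

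**What the visit does.** Protocol Section 5.6.1 is headed "End of Study Period 1 Follow-up Clinic Visit and Beginning of Study Period 2". At this visit the participant hands back one pump and receives the other.

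**Intended length.** Protocol Section 5.2.1 has "Study Period 1: 3-week period of PLGS (Group A) or SAP (Group B" and a matching line for Period 2. SAP Section 1 refers to "3-week study periods (21 days each". The sample size in Protocol Section 10.3 also assumes two 3-week periods.

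**Data used.** In the date-time table of SAP Section 4.3, Period 1 data stop at the earlier of 21 full days or "b) Date-time in which patient left clinic on Period 2 Initiation Visit". The Period 2 row counts its 21 days from the Period 1 Initiation Visit. A fallback table, for use when clinic departure times are missing, counts 22 days from each period's own starting visit. Neither table sets a minimum length. SAP Section 6.1 admits everyone with at "least one CGM sensor reading in each of the two treatment periods. No additional minimum amount of" CGM use.

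**The concern.** A site that follows Table 1 cannot end a period before day 21. A site that follows Section 5.5 can end it on day 14 and still comply. The two passages therefore allow different treatment durations in a crossover whose endpoint, hypotheses and sample size are all framed around 21 days.

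Three things are at stake.

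- **Precision and balance.** A short period supplies fewer readings, and one person's two periods may differ in length. Each person-period gives one percentage to the model, and no weighting by amount of data is stated, so a 14-day period counts as much as a 21-day one.
- **Deviation counts.** SAP Section 9.2 tabulates protocol deviations. An end visit on day 16 is out of window under Table 1 and in window under Section 5.5.
- **Scheduling.** Under Section 5.5 the end visit (day 14 to 28) overlaps the day-14 contact (day 11 to 17).

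**Working it through.** **1. The windows.**

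| Source | Earliest | Latest |
|---|---|---|
| Table 1, 21+7d | day 21 | 21 + 7 = day 28 |
| Section 5.5, 21 ± 7 | 21 − 7 = day 14 | 21 + 7 = day 28 |

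The gap is 7 days at the early end, or 7/21 = one third of the planned period.

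**2. Data in a short period.** Readings come every 5 minutes (Protocol Section 1.2), which is 288 a day.

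- 21 days: 21 × 24 = 504 hours, 6048 readings.
- 14 days: 14 × 24 = 336 hours, 4032 readings, one third fewer.

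The per-protocol threshold of 200 hours (SAP Section 5.2) would not pick this up. 200/336 = 59.5% of a 14-day period, so a participant with ordinary sensor wear passes.

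**3. The plan's own sample size.** Inputs: SD of paired differences 3%, two-sided alpha 5%, power 90% and 33% relative reduction (Protocol Section 10.3); control rate 4.0% (SAP Section 11).

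Formula: n = [SD × (1.960 + 1.282) / delta]².

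- delta = 4/3 = 1.333: n = 53.2, so 54.
- delta = 0.33 × 4 = 1.32: n = 54.3, so 55.

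The protocol states 52, so the figure is approximately reproduced. For power, Φ(delta × √N / SD − 1.960) at N = 90 gives 98.7% (delta 1.32) to 98.8% (delta 1.333), against the stated 99%.

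**4. An extreme bound on the loss.** The documents do not split the SD into components. Assume that all of the paired-difference variance (3² = 9) is sampling noise, shared equally by the two periods (4.5 each) and proportional to 1/days. A 14-day period then contributes 4.5 × 21/14 = 6.75.

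| Case | Variance | SD | N for 90% power | Power at N = 90 |
|---|---|---|---|---|
| Both periods 21 days | 4.5 + 4.5 = 9 | 3.00 | 54–55 | 98.7–98.8% |
| One of the two is 14 days, everyone | 4.5 + 6.75 = 11.25 | 3.35 | 67–68 | 96.2–96.5% |
| Both are 14 days, everyone | 6.75 + 6.75 = 13.5 | 3.67 | 80–82 | 92.6–93.1% |

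Ranges run over delta = 1.32 and 1.333. For the last row with delta 1.32: 1.32 × √90 / 3.674 = 3.41; 3.41 − 1.96 = 1.45; Φ(1.45) = 92.6%. Any part of the variance that does not shrink with more days, such as real differences between people in treatment effect, makes the loss smaller.

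**5. The SAP window against the visit.** In Period 1 a late visit is cut at 21 days and an early visit shortens the data. In Period 2 the date-time row, read literally, stops data 21 days after Period 1 began. If Period 1 lasts 21 days or more, no Period 2 data remain. If it lasts 14 days, 21 − 14 = 7 days remain. This cannot be what was meant, and it conflicts with the fallback table, which counts from the Period 2 visit.

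**The case against.** The discrepancy rests on one sign, and a slip in Section 5.5 is plausible. There the line follows three ± entries, while end-of-phase visits elsewhere in the protocol carry a one-sided + (10+4 and 14+3 days). A misprinted or misread sign cannot be excluded. It is not the likelier explanation, because the text keeps + and ± apart throughout, including within the one row of Table 1. Even if it is a slip, the rule that sites read is still stated two ways.

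The surrounding text also points to 21 days: the period definitions, the summary's clinic visits at 7 and 21 days, and the SAP overview. The window is best read as a scheduling tolerance. A reader might infer that 14-day periods were planned or common. The documents do not support that; they show only that Section 5.5 would permit one.

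The SAP foresees early visits through its earlier-of rule, and requiring only one reading per period is a deliberate intention-to-treat choice. Dropout and sensor gaps shorten data under either window. That stands: the lack of a minimum is not an error in itself. It does mean that nothing in the analysis offsets a short period.

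A reader might also suppose that SAP Section 4.3 limits both periods to 21 days, so that only the early side is open. As printed, the date-time table does this for Period 1 only.

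**Conclusion.** The concern holds as an internal inconsistency with a modest consequence. One operative rule is written in two incompatible ways. It decides whether a compliant period may end before day 21, and which end visits count as deviations.

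Two stronger conclusions are tempting and are not supported. The first is bias: the endpoint is a percentage of readings, so a shorter period does not by itself shift it. The second is loss of adequate power: about 93% at N = 90 requires every period to end on day 14 and all variance to scale as 1/days, both assumptions from outside the documents. Even then, power exceeds the 90% design target and the required N (80 to 82) is below the planned minimum of 90. The actual loss depends on how many visits are early, which the documents do not say.

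**What to change.** - **Protocol.** Reconcile Table 1 and Section 5.5 so that both print one window, consistent with the period length stated in Section 5.2.1. Which window applies is for the sponsor to settle and is not judged here.
- **SAP Section 4.3.** Check the data windows against the reconciled visit window. Correct the Period 2 date-time row, whose 21-day limit is anchored to the Period 1 Initiation Visit, and make it agree with the fallback table. State that periods shorter than 21 days enter as observed, if that is the intention.
- **SAP Section 9.2.** Name the window used to count visit deviations.

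The SAP's revision history puts version 1.2 at data closeout. If the visits are already complete, rewording will not change conduct. A short table of actual period length by period and treatment would then show whether the matter arose.

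The cost is wording in both documents and, optionally, one descriptive table. The endpoint, model and sample size do not change.
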